### **11.2.6.2 Duration of platelet response**

Summary statistics will be presented. The non-dosing period will be included in the evaluation of the duration of platelet response. This assessment will be performed for the R788 group, R788-R788 group, and P-R788 group.

### **11.2.6.3 Individual plots of platelet count**

A swimmer plot will be presented for the platelet count. Items to be presented graphically are as shown in “[11.2.1.6 Individual plots of platelet count](#).” The non-dosing period will be included in the duration of exposure. This assessment will be performed for the R788-R788 group and P-R788 group.

## 11.2.7 Evaluation in the entire study period

Applicable period: Entire study period excluding follow-up

### 11.2.7.1 Individual plots of platelet count

Individual plots will be presented for the change in platelet count in each subject. The horizontal axis represents the number of days from the first day of study drug administration in Period I. The plot will include all platelet count measurements obtained between the start of the screening period and the end or discontinuation of the study, including unscheduled measurements and measurements affected by rescue medications. In addition, the dose of R788, times of use of rescue medications, and types and doses of permitted concomitant ITP medications will be presented.

## 11.3 Subgroup Analysis of Efficacy

- 1) The analyses described in “[11.2.6.1 Platelet response rate](#)” will be performed for each line of therapy (2nd line, 3rd line or later).
- 2) At the first data cut-off, the analyses described in “[11.2.2.1 Achievement rates for platelet count-related endpoints](#)” will be performed, excluding subjects who are still in Period II.
- 3) Summary statistic of platelet count in “[11.2.1.4 Summary statistics of platelet count](#)” will be presented for responders and non-responders in stable platelet response. Additionally, medians and quartiles will be presented graphically for responders and non-responders in the R788 group, and for the placebo group.
- 4) For the data in Period I, the median platelet count after the administration of the investigational product will be calculated for each subject, and the summary statistics will be presented for the R788 group, for responders and non-responders in stable platelet response in the R788 group, and for the placebo group.

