## 6.3 Interim Analyses and Data Monitoring

### 6.3.1 Timing of analysis

#### 1) First data cutoff

After all subjects have completed Period I, the following data collected by the first data cut-off date will be analyzed for Period I, long-term treatment of R788, R788 treatment period, and the

- Period I data of all subjects
- Period II data of subjects who completed Period II
- Follow-up data of subjects who completed the follow-up period

2) Second data cutoff

After all subjects have completed the non-dosing period, all data collected by the second data cut-off date will be analyzed for Period I, long-term treatment of R788, Period II, non-dosing period, Period III, R788 treatment period, and the entire study period.

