#### **11.2.2.1 Achievement rates for platelet count-related endpoints**

The variables to be analyzed are as follows:

- Achievement rate of a platelet count of  $\geq 50000/\mu\text{L}$  at Weeks 12, 24, 36, 48, and 52
- Achievement rate of a platelet count of  $\geq 30000/\mu\text{L}$  and change from the baseline in platelet count of  $\geq 20000/\mu\text{L}$  at Weeks 12, 24, 36, 48, and 52 (for subjects with a baseline platelet count of  $< 15000/\mu\text{L}$ )

Achievement rates and their two-sided 95% CIs will be presented. All subjects who are not assessed as responders due to discontinuation or missing data will be considered as non-responders.

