## 16. Changes from the Protocol

### 16.1 Changes in Statistical Analysis Plan Version 1.0

- 1) In “[3 Analysis Group](#),” the “period I data of subjects who discontinued R788 treatment in Period I” were added to the evaluation during long-term treatment of R788.

Reason: The purpose of this analysis was to evaluate the efficacy and safety of R788 from the start to the end of treatment with the product. Therefore, it was considered appropriate to include subjects who discontinued Period I in the analysis.

- 2) In “[3 Analysis Group](#),” evaluation in the entire study period was added.

Reason: To evaluate platelet response throughout the entire period after study entry.

- 3) In “[5.9 Analysis Visits](#),” the baseline for change calculation was defined as Day 1 of Period I for all periods.

Reason: In the protocol, the baseline was defined as Day 1 of each period. However, it was considered appropriate to use the value not affected by study drug administration as the baseline value.

- 4) In “[6.3.1 Timing of analysis](#),” the scope of data to be cutoff was changed, and variables to be analyzed were clarified.

Reason: To include Period II data in the first data cutoff and the non-dosing period data in the second data cutoff. In addition, variables to be analyzed at the time of cutoff were clarified.

- 5) Evaluation of line of therapy-related variables was added to “[9.1 Subject Demographics](#),” and evaluation of achievement rate of platelet-related endpoints was added to “[11.2.6.1 Platelet response rate](#)” and “[11.3 Subgroup Analysis of Efficacy](#).”

Reason: To evaluate the effect of line of therapy on efficacy, as evaluated in the paper of foreign studies.

- 6) In “[7 Definition of Derived Data](#),” the definition of the start day of platelet response was changed to “the first day after the start of study treatment in each period on which a platelet count of  $\geq 50000/\mu\text{L}$  for at least 28 consecutive days without the use of rescue medications was achieved.”

Reason: To evaluate stable maintenance of platelet count.

- 7) In “[11.1 Primary Endpoint](#),” sensitivity analysis of the primary endpoint planned in the protocol was deleted.

Reason: A blind review confirmed that no subject would need imputation of missing

platelet count data for the evaluation of stable platelet response. It was thus decided not to perform sensitivity analysis because no imputation would be performed.

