## **16.2 Changes in Statistical Analysis Plan Version 2.0**

1) In [“8.2 Discontinuation and Reasons for Discontinuation,”](#) the “Ongoing” category was added.

Reason: To clarify the number of ongoing subjects at the time of data cutoff.

2) In [“11.2.7.1 Individual plots of platelet count,”](#) the statement was changed to include permitted concomitant ITP medications used outside the treatment period in the figure.

Reason: To allow permitted concomitant ITP medications discontinued during the screening period to appear on the figure.

3) In [“11.3 Subgroup Analysis of Efficacy,”](#) the analysis of [“11.2.2.1 Achievement rates for platelet count-related endpoints”](#) excluding ongoing subjects was added.

Reason: To perform the analysis after excluding subjects who are still on long-term treatment at the time of data cutoff.

4) In [“13.1.1 Plasma Concentration,”](#) the statement on evaluation time point 2 was changed to include pre-dose data obtained on pharmacokinetic sampling days in the analysis.

Reason: To align the analysis with [“13.1.3 Scatter plots of plasma concentrations.”](#)

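### At the first data cutoff, both planned versions of the long-term response rate are biased low at Weeks 36, 48 and 52; at Weeks 12 and 24 only the version without subjects still in Period II is low.

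*SAP*

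**What the plan says.** **Timing and data.** Under SAP 6.3.1 the first cutoff comes "After all subjects have completed Period I". It takes Period I data from everyone, but from Period II only "Period II data of subjects who completed Period II".

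**Population.** SAP 3 puts every R788 subject's Period I data into the long-term evaluation. SAP 16.1 explains that "it was considered appropriate to include subjects who discontinued Period I in the analysis".

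**All-subject version.** SAP 11.2.2.1 gives response rates "at Weeks 12, 24, 36, 48, and 52", with the rule "All subjects who are not assessed as responders due to discontinuation or missing data will be considered as non-responders". It makes no exception for a visit that is not yet due.

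**Excluding version.** For the first cutoff only, SAP 11.3 2) says that the same analyses "will be performed, excluding subjects who are still in Period II". SAP 16.2 gives the reason: "To perform the analysis after excluding subjects who are still on long-term treatment at the time of data cutoff".

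**Later analysis.** SAP 6.3.1 then states: "After all subjects have completed the non-dosing period, all data collected by the second data cut-off date will be analyzed". Long-term treatment is among the evaluations listed there.

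**The concern.** A late enrollee who is doing well on R788 has no Week 52 result at the first cutoff. The all-subject version calls that subject a failure. Because 6.3.1 does not admit Period II data of ongoing subjects, it does so even at Week 36 when a response has already been recorded.

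The excluding version was added to deal with this, but it selects on outcome. Lack of efficacy is a withdrawal reason (Protocol 5.3.1). Of two subjects enrolled on the same late date, the one who failed and left stays in the denominator as a non-responder, and the one who responded and continued is removed.

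The rates serve the first-listed secondary objective, maintenance of platelet count during long-term treatment (Protocol 3.2), and comparison with the overseas studies (Protocol 4.1.2). If both versions err in the same direction, printing them side by side does not bracket the true value.

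**Working it through.** **Inputs from the documents.** 16 planned R788 subjects (Protocol 8.9.1); the cutoff, population and scoring rules above. The plan states no figure for the long-term rates, the accrual period, the number ongoing at cutoff or the exit rate. Its one design figure, an 89% chance that the R788 point estimate exceeds placebo, reproduces as 89.3% by exact binomial enumeration (16 versus 8 subjects, 17.8% versus 2.0%). It has no bearing on this point.

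**Notation.** N = R788 subjects; D = stopped in Period I; C = N − D = will complete Period II; r = Week 52 responders, all among C; f = share of completers who have reached Week 52 by the cutoff. Entry date is taken as independent of outcome.

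- True rate: r/N
- All-subject version: f·r/N
- Excluding version: f·r/(f·C + D)
- Enrolment-date denominator: f·r/(f·N) = r/N

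The all-subject version is low whenever f < 1. The excluding version is low when f(C + D) < f·C + D, that is, when f·D < D. It therefore needs at least one ongoing and one stopped subject.

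**Worked case (assumed).** N = 16, D = 8, C = 8, r = 4; true rate 4/16 = 25.0%.

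| f | All-subject | Excluding |
|---|---|---|
| 0.25 | 1/16 = 6.3% | 1/10 = 10.0% |
| 0.50 | 2/16 = 12.5% | 2/12 = 16.7% |
| 0.75 | 3/16 = 18.8% | 3/14 = 21.4% |
| 1.00 | 4/16 = 25.0% | 4/16 = 25.0% |

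At f = 0.50 the enrolment-date denominator gives 2/8 = 25.0%.

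**Weeks 12 and 24.** Everyone is past Period I, so the all-subject version is complete. If the same four subjects respond at Week 24, it gives 4/16 = 25.0%. The excluding version at f = 0.50 gives 2/12 = 16.7%.

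**Early-transition subjects.** An R788 subject who fails Period I may transition early and so is literally in Period II. If a share g of the D stoppers is removed on that ground, the excluding version becomes f·r/(f·C + (1 − g)·D), which is still low while 1 − g > f. Early transition comes after Week 12 of a 24-week period and its Period II lasts 28 weeks (Protocol 8.2, 8.3.1), so it ends by about Week 52. These subjects leave Period II no later than completers with the same entry date. The bias shrinks but is not expected to reverse.

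**Simulation (all rates assumed).** 16 subjects, uniform accrual, cutoff at the last subject's Week 24; 25% stop in Period I (70% of them transition early), 10% stop in Period II, half of completers respond. True rates: 0.65 × 0.5 = 32.5% at Week 52 and 0.75 × 0.5 = 37.5% at Week 24. In the excluding columns, the first figure keeps early-transition subjects and the second removes those still in Period II.

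| Accrual (weeks) | Week 52 all-subject | Week 52 excluding | Week 24 excluding |
|---|---|---|---|
| 39 | 7.1% | 15.7% / 20.6% | 22.1% / 29.2% |
| 52 | 13.0% | 22.5% / 26.3% | 28.3% / 33.1% |
| 104 | 21.7% | 28.4% / 30.3% | 33.7% / 35.8% |

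The all-subject version at Week 24 returns 37.5% throughout. With no discontinuations and a true rate of 30%, the excluding version returns 30% and only the all-subject version is low.

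**A milder set of assumptions.** True rate 20%, 50% to 80% of non-responders leaving Period I. With 104 weeks of accrual the Week 52 results are 15% (all-subject) and 16% to 19% (excluding). With 52 weeks the all-subject version gives 9% and the excluding version is as low as 11%. The enrolment-date denominator returns 20% in each case.

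**The case against.** The best case for leaving the plan alone is that these are interim, descriptive rates. SAP 6.5.2 treats everything but the primary endpoint as reference only, the long-term evaluation is repeated when nobody is left in Period II, and the Ongoing category in SAP 8.2 shows how many subjects are unfinished. The SAP never claims that the two versions bracket the truth. The simulated sizes rest on assumed accrual and exit rates; with 104 weeks of accrual the excluding version misses by one to four points, less than one subject in 16 (6.25 points). A smaller denominator also costs precision: the exact 95% interval for 3/16 is 4% to 46%, and for 2/7 it is 4% to 71%.

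All of that stands and limits the weight of the point. It does not make either rule right at Weeks 36 to 52. A count of ongoing subjects does not tell a reader which way the rates lean, and SAP 16.2 shows that the excluding version was added specifically to handle ongoing subjects.

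A reader might also infer that long-term safety at this cutoff omits events in subjects who stopped during Period II, because 6.3.1 names only those who completed it. The documents do not support going that far. SAP 8.2 tabulates discontinuations after transition to Period II, and the next bullet of 6.3.1 admits follow-up data, which such subjects provide. The bullet needs reconciling with 8.2; it does not establish a gap in the safety data.

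**Conclusion.** The point holds for Weeks 36, 48 and 52 at the first cutoff, where both versions are biased low. The all-subject bias needs only ongoing subjects who would respond. The bias in 11.3 2) also needs at least one stopped subject, and is smaller if R788 early-transition subjects are removed too, which the wording leaves open.

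It is tempting to conclude that neither version estimates any of the long-term rates. That is not so: at Weeks 12 and 24 the all-subject version is complete and unbiased, and only 11.3 2) is low. Nor does the point reach the primary endpoint, which uses Period I data, or the second-cutoff analysis.

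The size cannot be fixed from the documents. Under the assumptions shown, the shortfall runs from about one point (19% against 20%) to more than half of the true rate (9% against 20%, or 7.1% against 32.5%). The direction assumes only that entry date is unrelated to outcome.

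**What to change.** 1. Replace SAP 11.3 2) with a denominator set by enrolment date: all R788 subjects whose target day for the visit plus its window falls on or before the cutoff, whether continuing or stopped. With the SAP 5.9 windows (7 × week + 1, plus 7 days) these are Days 260, 344 and 372 for Weeks 36, 48 and 52. Count stoppers and R788 early-transition subjects as non-responders.
2. Report Weeks 12 and 24 on all R788 subjects only.
3. In SAP 6.3.1, either admit all Period II data up to the cutoff (completed, discontinued and ongoing), or admit data of subjects who completed or discontinued Period II and apply one Week 52 maturity rule to Weeks 36, 48 and 52. Without one of these, ongoing subjects who are mature for Week 36 or 48 would again be scored as failures. Either choice also reconciles 6.3.1 with 8.2.
4. If the first-cutoff tables already exist, label both versions as biased low for Weeks 36 to 52 and rely on the second cutoff.

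The cost is SAP wording and one rerun table. The Week 52 denominator falls to about 7 of 16 with 52 weeks of accrual (16 × 24/52 = 7.4) and about 12 with 104 weeks (16 × 76/104 = 11.7), taking the cutoff 24 weeks after accrual closes. Intervals widen accordingly.

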## 12. Safety

### 12.1 Adverse Events and Adverse Drug Reactions

Applicable period: Period I, long-term treatment of R788, Period II, non-dosing period, Period III, and R788 treatment period

The following analyses will be performed. For evaluation in the R788 treatment period, AEs and adverse drug reactions (ADRs) that occurred after administration of R788 will be included in the analysis.

#### 12.1.1 Incidence rates of adverse events and adverse drug reactions

The number of events, number of subjects with events, and incidence rates of events with two-sided 95% CIs will be presented. For Period I, the difference in incidence rates between groups and their two-sided 95% CIs will be presented.

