5.3 Withdrawal in Individual Subjects

5.3.1 Withdrawal criteria (withdrawal in individual subjects)

- 1) Adverse events
 - If the investigator judges that the adverse event requires withdrawal from the study.
 - If the subject does not wish to continue the study due to the adverse event.
- 2) Lack of efficacy (inadequate response)
 - If the investigator determines that there is an unacceptable risk for the subject to continue due to lack of efficacy of the study drug. The lack of efficacy of the study drug will be determined with reference to the following.

(1) Period I

- Subjects with a platelet count of $\geq 15000/\mu L$ on Day 1:
 - a) Platelet count of $< 50000/\mu$ L after Week 12 despite the increased dose to 150 mg *bid* for more than 4 weeks.
 - b) Platelet count of $< 50000/\mu$ L after Week 12 because of the inability to increase the dose to 150 mg *bid* due to possible poor tolerability.
- Subjects with platelet count of $< 15000/\mu$ L on Day 1:
 - a) Platelet count increase of $< 20000/\mu$ L from Day 1 after Week 12 despite the increased dose to 150 mg *bid* for more than 4 weeks.
 - b) Platelet count increase of $< 20000/\mu$ L from Day 1 after Week 12 because of the inability to increase the dose to 150 mg *bid* due to possible poor tolerability.
- Requirement for rescue therapy from Week 10 to platelet test at Week 24.
- (2) Periods II and III
 - Subjects who complete Period I:
 - a) Platelet count remains $< 50000/\mu$ L despite the increase dose to 150 mg *bid* for more than 4 weeks after the start of the study treatment in Period I.

b) Platelet count remains $< 50000/\mu$ L because of the inability to increase the dose to 150 mg *bid* due to possible poor tolerability.

- Subjects who meet all the "8.3.1 Transition criteria to Period II for subjects who withdraw from" (hereinafter referred to as early transition subjects):
 - a) Platelet count remains $< 50000/\mu$ L after ET Week 12 despite the treatment with 150 mg *bid* for at least 4 weeks after the start of the study treatment in Period II.
 - b) Platelet count remains at < 50000/µL after ET Week 12 because of the inability to increase the dose to 150 mg *bid* after the start of the study treatment in Period II due to possible poor tolerability.

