8.3.1 Transition criteria to Period II for subjects who withdraw from Period I

- 1) Subjects who meet any of the following criteria and withdraw from Period I due to "2) Lack of efficacy (inadequate response)" in "5.3.1 Withdrawal criteria (withdrawal in individual subjects)"
 - Subjects with a platelet count of $\geq 15000/\mu L$ on Day 1:
 - a) Platelet count of $< 50000/\mu$ L after Week 12 despite the increased dose to 150 mg *bid* for more than 4 weeks.
 - b) Platelet count of $< 50000/\mu$ L after Week 12 because of the inability to increase the dose to 150 mg *bid* due to possible poor tolerability.
 - Subjects with platelet count of < 15000/μL on Day 1:
 - a) Platelet count increase of $< 20000/\mu$ L from Day 1 after Week 12 despite the increased dose to 150 mg *bid* for more than 4 weeks.
 - b) Platelet count increase of $< 20000/\mu$ L from Day 1 after Week 12 because of

the inability to increase the dose to 150 mg *bid* due to possible poor tolerability.

- 2) Subjects with systolic blood pressure of < 140 mmHg and diastolic blood pressure of < 90 mmHg on ET Day 1 whether or not the subject is receiving antihypertensive treatment
- 3) Subjects without the following laboratory abnormalities on ET Day 1:
 - White blood cell count $< 2000/\mu L$
 - Neutrophil count < 1000/μL
 - Lymphocyte count $< 750/\mu L$
 - Hemoglobin < 10 g/dL
- 4) Subjects without the following laboratory abnormalities on the last laboratory test before ET Day 1
 - ALT or AST $> 1.5 \times ULN$
 - Total bilirubin $> 1.5 \times ULN$
 - eGFR < 30 mL/min
- 5) Subjects who do not have significant infection, an acute infection such as influenza, or inflammatory process on ET Day 1.
- 6) Subjects who have not received blood or blood products within the 2 weeks prior to ET Day 1 (intravenous immunoglobulin or platelet transfusion are allowed if used for rescue therapy).

8.3.2 Rationale for transition criteria to Period II for subjects who withdraw from Period I

- 1) This criterion was set to include subjects who withdraw from Period I due to lack of efficacy.
- 2) to 5) These criteria were set to ensure the safety of subjects.
- This criterion was set to exclude the matters that might affect the efficacy evaluation of R788.

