## 3. Analysis Group

Unless otherwise specified, the analysis will be performed on the following subjects and data. For FAS analysis, “treated subjects” will be handled as “randomized subjects.”

- 1) Evaluation in Period I
  - R788 group: Period I data of subjects who received R788 in Period I
  - Placebo group: Period I data of subjects who received placebo in Period I
- 2) Evaluation during long-term treatment of R788
  - R788 group: The analysis will be performed on the following subjects and data:
    - Period I data of subjects who received R788 in Period I
    - Period II data of subjects who received R788 in Period I, completed treatment with R788 in Period I and transitioned to Period II (subjects on long-term treatment of R788)

3) Evaluation in Period II

- R788-R788 group: Period II data of subjects who received R788 in Period I and early transitioned to Period II after discontinuing Period I
- P-R788 group: Period II data of subjects who received placebo in Period I and transitioned to Period II

4) Evaluation in non-dosing period

- R788 group: Non-dosing period data of subjects who transitioned to the non-dosing period (subjects who transitioned from Period II to Period III without non-dosing period are excluded).

5) Evaluation in Period III

- R788 group: Period III data of subjects who transitioned to Period III

6) Evaluation in R788 treatment period

- R788 group: The analysis will be performed on the following subjects and data:
  - Data from Period I, Period II, and Period III of subjects who received R788 in Period I
  - Data from Period II and Period III of subjects who received placebo in Period I and transitioned to Period II

7) Evaluation in the entire study period

- R788-R788 group: Data from Period I, Period II, non-dosing period, and Period III of subjects who received R788 in Period I
- P-R788 group: Data from Period I, Period II, non-dosing period, and Period III of subjects who received placebo in Period I

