## 4. General Principles of Statistical Analysis

- Statistical tests will be performed using a two-sided significance level of 5%.
- Summary statistics will include the number of subjects, mean, standard deviation, minimum, median, maximum, and quartiles.
- Unless otherwise specified, data will be summarized for each analysis group, each period, and each analysis visit.
- For confidence intervals (CIs) of proportions, Clopper-Pearson exact two-sided 95% CIs will be presented for each group, and Chan-Zhang exact two-sided 95% CIs will be presented for between-group differences.

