### **12.1.5 Early occurrence of adverse events and adverse drug reactions**

Applicable period: Period I, R788 treatment period

The variables to be analyzed are as follows:

- AEs and ADRs occurring up to Week 4 (Day 29)
- AEs and ADRs of interest occurring up to Week 4 (Day 29)
- AEs and ADRs occurring up to Week 12 (Day 85)
- AEs and ADRs of interest occurring up to Week 12 (Day 85)

The number of events, number of subjects with events, and incidence rates of events will be presented overall and by primary SOC and PT.

For AEs and ADRs of interest, event categories will be presented instead of primary SOCs.

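### The Period I adverse-event difference compares crude incidences although exit after Week 12 depends on platelet response, so it can be biased, in a direction that varies by event type

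*SAP*

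**What the plan says.** SAP 12.1.1 presents the number of events, the number of subjects with events and incidence rates with CIs for AEs and ADRs. It adds one contrast: "For Period I, the difference in incidence rates between groups and their two-sided 95% CIs will be presented". These are proportions of subjects, not person-time rates. SAP 4 assigns Clopper-Pearson intervals to each group's proportion and says "Chan-Zhang exact two-sided 95% CIs will be presented for between-group differences".

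The data counted are limited to the period. SAP 3 defines the R788 group for this evaluation as "Period I data of subjects who received R788 in Period I", with a matching line for placebo. Events after an early move to open-label R788 therefore belong to Period II.

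Early exit depends on platelet response. Protocol 8.3.1 opens Period II to "Subjects who meet any of the following criteria and withdraw from Period I due to" lack of efficacy, where the platelet criterion is failed "after Week 12 despite the increased dose to 150 mg" bid, or where that increase was not tolerated. Protocol 5.3.1 makes the exit a matter of judgement: "If the investigator determines that there is an unacceptable risk for the subject to continue due to lack of efficacy of the study drug". The rule is the same in both blinded arms.

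SAP 12.1.5 tabulates Period I AEs and ADRs up to Week 4 (Day 29) and Week 12 (Day 85), but specifies no between-group difference or CI. SAP 10.1 and 10.2 summarise Period I exposure. No exposure-adjusted AE rate appears anywhere in SAP 12.1.

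**The concern.** A crude incidence depends on how long each subject is watched. If one arm loses more of its subjects after Week 12, that arm has less time in which a first event can be counted, and the difference mixes drug effect with follow-up time. Here the reason for leaving is the outcome that the drug is meant to change, so unequal follow-up is foreseeable.

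The 12.1.1 difference is the only between-group AE estimate with a CI in the plan. The analyses by onset time (12.1.6) and by dose (12.1.7) cover the R788 treatment period and have no placebo comparator. The contrast is attached to the window where follow-up can diverge. The Day 85 window, which ends at about the time early transition opens, has counts but no contrast.

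**Working it through.** **Inputs from the documents**
- Sample size 16 R788 and 8 placebo (Protocol 8.9.1).
- Planning rates for stable platelet response 17.8% and 2.0% (Protocol 8.9.2).
- Overseas incidences (Protocol 1.4.1): all AEs 83.3% (85/102) v 75.0% (36/48); treatment-related 58.8% (60/102) v 27.1% (13/48); diarrhea 31% v 15%; hypertension 28% v 13%.

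**Assumed, because the documents give no figure**
- A share f of non-responders leaves, the same f in both arms, 50% to 100%, at Week 12 or Week 16.
- Hazards are constant.
- Failure of stable response stands in for meeting the exit criteria. The two definitions are related but not identical.
- The overseas figures are treated as full 24-week incidences. Those studies also allowed early exit, so the figures are illustrative only.

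**The plan's own figure.** Protocol 8.9.2 gives 89% as the chance that the R788 response estimate exceeds placebo. The exact sum of P(X1/16 > X0/8) with p = 0.178 and 0.02 is 89.3%, so it reproduces. The documents give no figure for AE bias.

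**Who could leave.** Expected non-responders are 16 × 0.822 = 13.2 on R788 and 8 × 0.98 = 7.8 on placebo. The proportion is higher on placebo (98% v 82%); the count is higher on R788.

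**Follow-up.** If all non-responders leave at Week 12, mean exposure is:
- R788: 0.822 × 12 + 0.178 × 24 = 14.1 weeks
- Placebo: 0.98 × 12 + 0.02 × 24 = 12.2 weeks

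If half leave, it is 19.1 v 18.1 weeks.

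**Bias model.** With 24-week incidence P, incidence to week w is I(w) = 1 − (1 − P)^(w/24). If a fraction g of an arm leaves at week w, its crude Period I incidence is g·I(w) + (1 − g)·P, with g = 0.822f on R788 and 0.98f on placebo.

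All AEs, w = 12, f = 1:
- R788: I(12) = 59.2%; crude = 0.822 × 59.2 + 0.178 × 83.3 = 63.5%
- Placebo: I(12) = 50.0%; crude = 0.98 × 50.0 + 0.02 × 75.0 = 50.5%
- Crude difference 13.0 against a full 24-week difference of 8.3: bias +4.6 points (unrounded inputs)

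Treatment-related AEs, same setting:
- R788: I(12) = 35.8%; crude 39.9%
- Placebo: I(12) = 14.6%; crude 14.9%
- Crude difference 25.1 against 31.7: bias −6.7 points

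The sign turns on which arm loses more incidence. For all AEs, placebo loses 0.98 × 25.0 = 24.5 points and R788 loses 0.822 × 24.1 = 19.8. For treatment-related AEs, R788 loses 0.822 × 23.0 = 18.9 and placebo 0.98 × 12.5 = 12.2.

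| Bias in points | Wk 12, f = 100% | Wk 12, f = 50% | Wk 16, f = 100% | Wk 16, f = 50% |
|---|---|---|---|---|
| All AEs | +4.6 | +2.3 | +3.2 | +1.6 |
| Treatment-related | −6.7 | −3.3 | −3.7 | −1.9 |
| Diarrhea | −4.5 | −2.3 | −2.8 | −1.4 |
| Hypertension | −4.4 | −2.2 | −2.8 | −1.4 |

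If every first event fell before Week 12, the bias would be zero.

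**Common window.** Up to Week 12 the same model gives 59.2% v 50.0% (difference 9.2) for all AEs and 35.8% v 14.6% (difference 21.2) for treatment-related AEs. Lack-of-efficacy exit at or after Week 12 has essentially no effect on these figures.

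**Scale.** One placebo subject is 1/8 = 12.5 points. An illustrative 13/16 v 6/8 gives a difference of 6.3 points with a Newcombe 95% CI of about −24 to +42. Newcombe is used here only as a stand-in for Chan-Zhang.

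**The case against.** The strongest reply is that the plan already holds most of what is needed and that the stakes are low. SAP 12.1.5 gives Period I counts to Day 85, from which a reader can compute a difference. SAP 10.1 gives exposure by group, so a crude event rate per patient-week can be assembled from planned outputs. The AE difference carries no test, SAP 6.5 treats everything beyond the primary endpoint as reference, and the CI dwarfs the bias.

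Much of this stands, and it is why the point concerns supplementary results. Three things remain. Rates of first events per patient-week cannot be rebuilt from the planned summaries. The Period I exposure bands in SAP 10.2 end at 12 weeks or more, which puts Week 12 leavers together with 24-week completers. And a contrast left for readers to compute is not a specified result.

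A second reply is that the Week 12 window is not clean either. That is right. Withdrawal for AEs or by request can happen at any time, Protocol 5.3.1 lists rescue from Week 10 among the guides to lack of efficacy, and the Week 12 visit may fall on Days 82 to 88. The window also drops later randomised data, and because dose escalation is possible only from Week 4 it contains less time after escalation. These are reasons against making Week 12 the main contrast, not against showing its difference.

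**Conclusion.** The Period I difference in SAP 12.1.1 can be biased by unequal follow-up, and the plan has no contrast that addresses this. At the protocol's response rates the shift is about +2 to +5 points for all AEs and about −2 to −7 for treatment-related AEs. Both ranges rest on assumed exit shares, equal exit among non-responders in the two arms, and constant hazards. Both are small beside the uncertainty with 16 v 8 subjects.

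A reader might infer more: that failures are mostly on placebo, so the comparison predictably overstates the R788 excess, perhaps by 10 points. The documents do not support that.
- By count, more failures are expected on R788, and the exit rule is identical in both arms.
- The 10 points needs equal hazards (75% in each arm) and 90% of placebo but only 50% of R788 subjects leaving at Week 12, giving 52.5% v 62.5%. That means 0.90/0.98 = 92% of placebo non-responders leave against 0.50/0.822 = 61% of R788 non-responders, a gap that no figure in the documents supports. Under equal hazards, a 98/82 split gives about +4.
- The same 90/50 split applied to the treatment-related incidences gives −0.3 points, and 98/82 gives −6.6.
- Withdrawals for AEs, if commoner on R788, would push against overstatement.

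The supported conclusion is possible bias whose sign depends on event type, event timing and who leaves.

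**What to change.** Keep the 24-week difference in SAP 12.1.1 as it is, and add two supplementary results:
1. In SAP 12.1.5, for Period I, give the between-group difference in overall AE and ADR incidence up to Week 12 (Day 85) with its Chan-Zhang exact 95% CI.
2. Beside SAP 12.1.1, give exposure-adjusted rates by group for AEs and ADRs: all events, and first events, per 100 patient-weeks. Count person-time for first events only up to the event.

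State in the text that the 24-week difference may reflect unequal follow-up and that the direction is not known in advance.

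The cost is a few more columns from data already collected, with no change to trial conduct. Fewer events will have occurred by Week 12, so that CI will not resolve much, and person-time rates assume a roughly constant hazard. Neither result should replace the 24-week comparison.
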